3.4.2 EXCLUSION CRITERIA.....	15
3.4.3 SAMPLE SIZE CALCULATION	15
3.5 DATA COLLECTION METHODS	15
3.6 ANALYSIS.....	16
4.0 WITHDRAWAL CRITERIA FOR STUDY PROGRAMME	17
5.0 DATA MANAGEMENT FOR STUDY PROGRAMME	17
5.1 PROCEDURE FOR ACCOUNTING FOR MISSING, UNUSED, AND SPURIOUS DATA.	18
5.2 PROCEDURES FOR REPORTING ANY DEVIATION(S) FROM THE ORIGINAL STATISTICAL PLAN	18
5.3 ARCHIVING	19
6.0 REGULATORY ISSUES.....	19
6.1 ETHICS APPROVAL	19
6.2 ETHICAL ISSUES	19
6.3 CONFIDENTIALITY	20
6.4 INDEMNITY	20
6.5 SPONSOR.....	20
6.6 MONITORING, AUDIT & INSPECTION	20
7.0 STUDY MANAGEMENT	21
7.1 STUDY MANAGEMENT GROUP	21
8.0 DISSEMINATION AND PUBLICATION POLICY	21
9.0 FUNDING	22
10.0 IMPACT	22
11.0 REFERENCES	24

Study Summary

TITLE	Further validation and determination of the Minimum Clinically Important Difference of a scale to measure quality of life in patients with severe asthma
DESIGN	A multi-centre mixed methods study of a new asthma specific quality of life questionnaire including limited clinic data, using the UK Severe Asthma Network.
AIMS	To collect further quantitative data to validate a new asthma quality of life scale, the Severe Asthma Questionnaire (SAQ). To determine the Minimum Clinically Important Difference (MCID) of the SAQ
OUTCOME MEASURES	
Questionnaires:
 
 1. The Severe Asthma Questionnaire (SAQ) 2. The Mini Asthma Quality of Life Questionnaire (MiniAQLQ) 3. The EQ-5D-5L 4. The Asthma Control Test (ACT)/ Asthma Control Questionnaire (ACQ) 5. Global Rating of Change Questionnaire (GRCQ) 6. Clinical data comprises: 7. Spirometry 8. BMI 9. Asthma severity 10. Health care utilisation: ED attendance in the last 12 months, Hospital admissions in the last 12 months; 11. Number of exacerbations in the last 12 months requiring OCS Prednisolone dose mg/day (if oral steroid dependent).
POPULATION	All patients aged 16 years or over, who have attended one of three participating UK specialist asthma centres for the validation study and with data also collected from Derriford Hospital's Chest Clinic (DHCC) for use in determining Minimum clinically Important difference.
ELIGIBILITY	Over 16 years of age Diagnosis of Severe Asthma
DURATION	18 months
REFERENCE DIAGRAM	Gantt chart (Appendix 1)

1. Introduction

1.1 Background

The global prevalence of asthma is estimated to be 300 million and is expected to grow by more than 100 million by 2025 [1]. Patients with severe and difficult-to-treat asthma comprise a small proportion (5-10%) of all asthmatic patients, yet are responsible for a disproportionate degree of asthma morbidity and costs [2]. These patients have ongoing daily symptoms despite maximal medical therapy and are more likely to be admitted to hospital and to access out of hours' emergency healthcare than asthmatics with mild or moderate disease [2].

Corticosteroids have proved extremely effective in the acute and chronic treatment of inflammatory diseases. However, despite their clinical success, oral corticosteroids (OCS) have many known side effects which limit their tolerability, particularly in the long term [3]. As the multi-faceted negative consequences of OCS therapy are becoming better understood, the drive to find OCS substitutes becomes more urgent. However, in order to fully appreciate the value of steroid sparing agents which tend to be more expensive than OCS, the wider picture of OCS adverse effects must be considered to determine the real cost offsets achievable by such therapies.

While patients with mild and moderate asthma can usually be controlled using inhaled medication, in severe asthma OCS are often required. OCS exposure may be significant through either frequent short courses for exacerbations or as a maintenance dose. Studies on patients with mild and moderate asthma show that exacerbations are predicted by non-asthma related health problems [4] and by poor adherence [5]. In mild and moderate asthma, adherence to inhaled corticosteroids is affected by real or perceived medication side effects [6,7]. There is limited understanding of this relationship in severe asthma patients; qualitative data suggests that side effects impact on OCS use [7], but the relationship between OCS and inhaled medication adherence is complex [8]. Patients' concerns differ from those of clinicians [7,8]. The consequences of poor adherence for those with severe asthma are extremely serious and include frequent disabling attacks, recurrent unpredictable admissions and death.

While the consequences of non-adherence to OCS in patients with severe asthma may be dire, so too are the perceived side-effects. Of major concern to patients are changes in facial and body appearance, weight gain, gastro-oesophageal reflux, mood changes and sleep disruption. Metabolic changes including high blood pressure, precipitating diabetes mellitus and long-term effects on bone are of more concern to clinicians.

Health-related quality of life (HRQoL) is one of several outcome measures used to inform treatment guidelines and economic decision-making for the treatment of asthma. HRQoL scales are important amongst outcome measures in that they inform whether treatment is worthwhile from the perspective of the patient, a perspective that includes the burden of disease and the burden of treatment. Asthma varies in severity, and increased doses or types of medication are required for the more severe patients. Severe asthma patients have uniquely different types of HRQoL deficits and in this population the

burden of treatment, particularly with OCS, becomes a larger determinant of HRQoL. The impact of OCS is known to be far greater than the impact of other asthma treatments [8], and therefore, severe patients, i.e. those exposed to high doses of OCS, are likely to have a greater treatment burden than other patients.

Novel biologic agents are likely to become increasingly available to treat severe asthma. While these are more expensive than conventional treatments, if effective they may reduce symptoms, health care costs and reduce the need for oral steroids. In order to understand the impact of these newer drugs, measures must be used to accurately reflect the specific issues of severe asthma burden, including the burden of treatment. Previous work has demonstrated that existing asthma-specific scales underestimate the burden of severe asthma, in particular treatment with OCS, and therefore will underestimate the benefits of steroid sparing agents [8]. Improved assessment procedures are needed to provide accurate information on which treatment and resourcing decisions are made.

Research into severe asthma is limited by the lack of questionnaires suited to this population that capture both the health deficits experienced by severe asthma sufferers and the range of adverse experiences from treatment. It is therefore important that appropriate outcome and adherence measures are available to assess service development in relation to severe asthma. As a first step in questionnaire development, in-depth interviews were held in a sample of 23 patients attending the difficult asthma service at Derriford Hospital. These interviews revealed the substantial burden of symptoms associated with OCS that were not addressed by existing measures of health-related quality of life (HRQOL) [8].

The importance of such measures is emphasised by two major reports. The National Institute for Health and Care Excellence (NICE) is strongly supportive of the need for improved measurements which reflect the patients' burden in severe asthma and the impact of OCS [9]: "the Committee concluded that other adverse effects (of oral steroids), such as obesity, hypertension, mood changes, depression, psychosis, thinning skin, delayed wound healing, reduced growth in children and increased risk of infection were additional important factors that had not been captured when calculating the quality adjusted life years."

When statutory bodies such as NICE compare the cost effectiveness of very cheap OCS versus novel biologic agents, it is possible to conclude that such treatments may not meet the Incremental Cost-Effectiveness Ratio (ICER), particularly when compared to OCS. Only if the burden of OCS is accurately measured can the real cost effectiveness be established.

In a qualitative study [8] in-depth interviews were held in a sample of 23 patients attending the difficult asthma service at Derriford Hospital. The main health deficits and burden of treatment were defined and compared to existing questionnaires. We found just how much patients suffer from side-effects of long-term oral steroids and how these are poorly captured by existing scales. The National Review of Asthma Deaths [10] showed that asthma has many preventable factors, in particular, poor use of preventer medication. In addition, psychosocial factors such as depression contributed to the cause of death in 25% of cases. OCS have profound psychosocial impacts. Since the publication of this report, there has

been increasing interest in identifying people at risk of asthma deaths, improving services for patients with severe asthma, and rational use of new treatments.

The SAQ questionnaire was derived from a qualitative study [8] and questions and design were evaluated by a panel of international expert clinicians. The concepts and wording were modified and tested in an iterative series of four focus groups of patients attending the difficult asthma service [9]. The questionnaire was then field tested in 160 patients and compared to the MiniAQLQ, the Asthma Control test and clinic data including BMI, lung function, and health care consumption [10]. The final version takes into account the lessons learned from this quantitative study and further input from the panel of experts.

The SAQ questionnaire has 16 questions rated on a 0-6 Likert scale and on a 0-100 scale rating of (i) overall quality of life (ii) how your asthma symptoms and the side effects of your medicines have affected your quality of life during the last two weeks.

1.2 Rationale For Current Study

This research is the continuation of a project which provided preliminary validation of the SAQ. Whilst the preliminary validation provided evidence for the validity of the SAQ, a limited sample size made comparisons between groups of participants difficult. In addition, all data were collected in the South West of England (Plymouth, Devon), which may limit the studies generalisability to the rest of the UK. This further validation study will address these two issues by collecting more data from multiple centres around the UK. The second part of this research will collect data for the calculation of the SAQ's Minimum clinically Important difference (MCID). This value is required if the SAQ is to be useful in clinical practice, clinical trials and research.

Research into the burden of severe asthma, in particular treatment with OCS, is limited by the lack of questionnaires suited to this population that capture both the health deficits experienced by severe asthma sufferers, and the range of adverse experiences from treatment. As a consequence, the benefits of steroid sparing agents are underestimated [8].

NICE has called for such a questionnaire to measure the impacts on patients of severe asthma and its treatment. The new biological treatments which are already developed or in the pipeline need to be tested with measures which reflect their impact specifically on people with severe asthma [11]. Content validity of the SAQ has been established through the qualitative studies as recommended by the FDA [12].

The aim of this study is to provide further construct validity for the SAQ using UK collaborators. This will be done by showing that the SAQ is sensitive to differences in treatment, symptomatology, as well as being able to detect changes in patients' HRQOL after the commencement of a new treatment for severe asthma.

1.3 Patient And Public Involvement

Patients have been involved in the development of this questionnaire since the beginning of the research. As part of an initial study to identify the burden associated of living with severe asthma, qualitative interviews were conducted. In total 23 patients diagnosed with severe asthma were interviewed, and highlighted the burden they experienced as a result of taking OCS [8].

Furthermore, four focus groups were conducted in which patients were presented with a draft version of the Severe Asthma Questionnaire (SAQ). In total 16 patients diagnosed with severe asthma were recruited [9]. These patients gave substantial feedback concerning the wording of questions and the response scale used on the questionnaire. Participants also suggested the addition of new items to the questionnaire, in order to better capture the burden associated with their disease or OCS.

After gaining feedback from a panel of international expert clinicians, the wording of an item in the SAQ was changed to reflect a timescale of months, rather than seasons. This change was made in order to make the questionnaire internationally applicable, including in countries where they do not have four seasons.

It was decided by the SAQ development team that this constituted a significant change to the questionnaire. Therefore, this final version of the SAQ was also presented to four patients diagnosed with severe asthma, to check that this change had not altered the ease at which the focus group patients had understood the wording of the original questionnaire item.

Moreover, as this occurred in a clinic setting, this enabled us to ensure that patients found the SAQ as easy to complete in a clinic setting, which has considerable time constraints, compared to during the focus groups, where time was not a concern. Overall, these four patients reported that the final version of the SAQ was easy to comprehend and complete before their clinic appointment.

Potential logos for the SAQ were also discussed with five patients diagnosed with severe asthma, whilst they waited for their clinic appointment. The final logo was chosen as it was described as distinguishing the questionnaire from others. The patients' choice of logo was also considered by three specialist asthma nurses, who agreed that it would increase the chance of identifying the SAQ under the time constraints of day to day clinical practice.

Finally, the design and concept of the questionnaire and this study were discussed with the Plymouth Breathe Easy group of the British Lung Foundation who provided positive comments (7.2.17). These varied and extensive forms of qualitative evaluation were carried out in order to ensure content validity of the scale as defined by the FDA, where it is asserted that "Content validity is supported by evidence from qualitative studies that the items and domains of an instrument are appropriate and comprehensive relative to its intended measurement concept, population, and use. Content validity is specific to the population, condition, and treatment to be studied [12].

2.0 National Validation Study

2.1 Aim

To further validate the SAQ for use in the United Kingdom.

2.2 Objectives

To collect data from patients attending the UK specialist Asthma centres:

To provide a description of the factor structure of the SAQ and to demonstrate equivalence across populations.

To show that the SAQ correlates in an acceptable manner with the Mini Asthma Quality of Life Questionnaire (MiniAQLQ) and EQ-5D-5L (EQ5D)

To show that the SAQ is a discriminator of patients who have different frequencies of exacerbations and different levels of prednisolone consumption.

To show that the SAQ is equivalent in discrimination for exacerbations to the MiniAQLQ or EQ5D but is a better discriminator than these questionnaires for treatment levels of oral corticosteroids.

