2.3 Study Design

Type of study: A multi-centre, cross-sectional study of four questionnaires including clinic data.

Duration of the study: 12 months.

Sample size: 80 – 107 participants from each of the three centres (N= 240 - 321):

Royal Brompton and Harefield NHS Foundation Trust, London, UK

Birmingham Heartlands Hospital NHS Foundation Trust, Birmingham, UK

University Hospital of South Manchester, Manchester University NHS Foundation Trust, UK

Royal Devon and Exeter Hospital NHS Foundation Trust, Exeter, UK

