2.6.3 Sample size calculation

Sample size determination is based on the analysis where the greatest number of patients is needed, namely factor analysis. For exploratory factor analysis the number of participants needed per item varies but ranges between 15 and 20 participants per item [18, 19]. There are 16 items in the SAQ. Thus, data from 240 – 320 participants is needed for any factor analysis, (80 – 107 participants from each centre.)

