2.8 Analysis

Factor analysis of the SAQ A trial principal axis factor analysis with scree plot will be calculated. On the basis of factor loadings on the first factor, it will be decided whether it is legitimate to provide an overall score for the questionnaire. Using the scree plot to determine factor number, an oblique rotation will be carried out and interpretation of emerging factor loadings (from the pattern matrix) determined.

Correlations between questionnaires

Correlations between questionnaires will be calculated using Pearson Correlations.

Discriminant validity We will test for significant differences between the SAQ and other scales using a mixed design analysis of variance (one within and one between) where groups are defined in two ways (a) maintenance dose oral corticosteroids and (b) cumulative dose oral corticosteroids. The aim of this analysis is to investigate whether the SAQ has better discriminant validity than other scales. First the interaction term of the analysis of variance will be used to determine whether sensitivity differs across all groups. Second, because the SAQ is expected to be more sensitive to discrimination at the top end of prednisolone use, a mixed design analysis of variance will be conducted on the two highest doses of prednisolone only.

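### The objective of showing that the SAQ's factor structure is equivalent across populations has no analysis that could test it, and the populations are not defined

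*Protocol*

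**What the plan says.** Section 2.2 of the protocol gives the factor analysis two tasks in one objective: "To provide a description of the factor structure of the SAQ and to demonstrate equivalence across populations". The first is descriptive and the second is a claim to be proved. The word *populations* is not defined there or elsewhere.

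Section 2.8 then sets out the factor analysis. It begins: "A trial principal axis factor analysis with scree plot will be calculated". Loadings on the first factor decide whether an overall score is legitimate, and the scree plot fixes the number of factors. Finally, "an oblique rotation will be carried out and interpretation of emerging factor loadings (from the pattern matrix) determined". The other analyses in that section are Pearson correlations between questionnaires and mixed analyses of variance by oral corticosteroid dose. Neither concerns factor structure.

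Section 2.6.3 bases the sample size on exploratory factor analysis, where the requirement "ranges between 15 and 20 participants per item". It concludes: "Thus, data from 240 – 320 participants is needed for any factor analysis, (80 – 107 participants from each centre". Sections 3.2 and 3.5 add the Part 2 baseline questionnaires to the same dataset.

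Section 1.2 gives two reasons for the study. The earlier sample was too small for comparisons between groups, and all earlier data came from the South West of England, "which may limit the studies generalisability to the rest of the UK".

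**The concern.** A single factor solution with no grouping variable presupposes that the same items load on the same factors in everyone analysed. It describes the mixture. It gives no measure of how far one group's loadings differ from another's, and no rule for calling them equivalent. If section 2.8 is followed as written, the second half of the objective has no result behind it.

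Two things are at stake. The first is the claim that the SAQ behaves alike across the UK, since geography is one of the two stated reasons for going to more centres. The second is the overall score. The first factor decides whether that score is legitimate, and section 3.6 uses the mean of the 16 items as one of the two scores for the MCID. A report could present the combined solution as evidence of equivalence when it is not.

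**Working it through.** **1. The plan's own figure.** Inputs are the 16 items and the 15–20 participants per item in section 2.6.3, and the three centres in section 2.3.

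- Total = items × participants per item: 16 × 15 = 240 and 16 × 20 = 320.
- Per centre = total / 3: 240 / 3 = 80, and 320 / 3 = 106.7, rounded up to 107. Then 3 × 107 = 321, which is the upper total in section 2.3.

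The stated figures reproduce exactly. For one combined analysis the plan meets its own rule.

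**2. Objective against analysis.** Testing equivalence of structure needs a grouping variable, a measure of agreement between groups and a criterion. Section 2.8 names the extraction method, the rule for the number of factors, the type of rotation and the matrix to be read. It names none of those three.

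**3. What the numbers allow within groups.** Participants per item = n / 16. Part 2 contributes 30–50 per site (section 3.2). Rows that include Part 2 assume full recruitment and no patient counted in both parts.

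| Group | n | Per item |
|---|---|---|
| One centre, Part 1 only | 80–107 | 5.0–6.7 |
| One site in both parts | 110–157 | 6.9–9.8 |
| Plymouth (Part 2 only) | 30–50 | 1.9–3.1 |
| Earlier field-test sample (section 1.1) | 160 | 10.0 |

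Section 3.4.3 implies about 25 Part 2 patients per site instead. A site in both parts would then have 105–132, or 6.6–8.3 per item.

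**4. Two broad groups.** Take the South West as Plymouth and Exeter, against London, Birmingham and Manchester. Section 2.3 speaks of three centres but lists four hospitals, including Exeter, so both readings are shown, with Part 2 at 30–50 per site.

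- *Part 1 total of 240–320 spread equally over four hospitals (60–80 each).* South West: 60 + 30 + 30 = 120 to 80 + 50 + 50 = 180, or 7.5–11.3 per item. Rest: 3 × (60 + 30) = 270 to 3 × (80 + 50) = 390, or 16.9–24.4 per item.
- *Exeter in Part 2 only.* South West: 30 + 30 = 60 to 50 + 50 = 100, or 3.8–6.3 per item. Rest: 3 × (80 + 30) = 330 to 3 × (107 + 50) = 471, or 20.6–29.4 per item.

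The larger group is well supplied. The smaller group limits the precision of any comparison.

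**The case against.** The strongest reply is that section 2.8 is an outline. The SAP is not shown, and the statistic and threshold for a group comparison are details it could supply. The protocol does not call the analysis pooled either; that is inferred from the single analysis and the summed sample size. This stands to the extent that one cannot say equivalence will never be tested. But section 2.8 is specific about every other factor-analytic step, and the sample size was justified only for one exploratory analysis. The mismatch between objective and analysis is in this document.

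Three stronger readings are tempting and are not supported:

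- *That the per-centre numbers breach the plan's own rule.* Section 2.6.3 applies 15–20 per item to the total, which meets it. The 80–107 is that total divided by three, and no per-centre exploratory analysis is promised. The rule is for exploratory analysis and does not settle the size needed for a congruence or multi-group comparison.
- *That merging Part 2 baselines destroys the contrast between the South West and the rest.* Section 5.0 gives each site its own participant-number prefix, so the groups can be separated.
- *That *populations* must mean centres.* Sections 1.1 and 1.2 equally allow the new UK sample against the earlier 160 patients. On that reading, combining the new centres is proper and the per-centre counts do not matter. There is still no comparison planned.

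**Conclusion.** The point holds as a mismatch between an objective and its analysis. The protocol undertakes to show equivalence of factor structure and specifies one ungrouped exploratory solution, which cannot show it on any reading of *populations*. The combined description of the factor structure remains valid, and 240–320 is correctly derived for it.

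The size of the problem lies in what the data could support if a comparison were added. There are about 5–7 participants per item in a centre, or about 7–10 at a site in both parts. The second range assumes that Part 2 recruits 30–50 per site with no overlap. Separate exploratory solutions by centre would be imprecise. These counts show that no between-group comparison was provided for; they are not a breach of the plan's rule or an error in the sample size.

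**What to change.** Define *populations* in section 2.2. A workable choice is South West sites against the rest, formed from the site prefixes in section 5.0. If the earlier field-test sample is meant, say so, and confirm that its item-level data and questionnaire version are comparable.

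Keep the combined solution in section 2.8 and add one pre-specified comparison of factor structure. For example:

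- extract the number of factors found in the combined solution separately in each of the two broad groups;
- align each to the combined solution, so that differences in rotation are not taken for differences in structure;
- report Tucker's congruence of the loadings between groups for each factor, with bootstrap confidence intervals from resampling patients within group;
- set the threshold before the data are seen, and claim equivalence only if it is met.

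State the expected size of the smaller group and the reason it is thought sufficient, because the per-item rule does not answer that.

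If the sponsor does not want this analysis, or the threshold is not met, narrow the objective to describing the SAQ's factor structure.

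The cost is one further analysis of data already being collected, with no extra patients. The downside is that the result may be too imprecise to support an equivalence claim, particularly if the South West group is small.
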